### 3.5 Scope of Application and the Relevant Information

#### 3.5.1 Intended Purpose

Restylane Skinboosters Vital Lidocaine is for aesthetic use to improve appearance of dorsal hands. The addition of lidocaine provides a pain-relieving effect during treatment.

#### 3.5.2 Indication and Target Population

This product is intended for injection in the dorsal hand to improve its appearance by increasing

	Title 43CH2305 CSP Vital-Lido-Hand-2w	Doc id MA-57336
--	---	---------------------------

the tissue volume in subjects over the age of 18. It should be injected in the dermal layer of the skin, preferably in the deeper part of dermis. The addition of lidocaine is intended to increase overall treatment comfort.

The products shall not be used in patients under 18 years of age.

### 3.5.3 Intended Users

Injections of Restylane Skinboosters Vital Lidocaine must only be done by plastic surgeons, dermatologists and cosmetic doctors at hospitals and medical plastic surgery institutions officially approved by the administrative authorities. These institutions include clinics for medical cosmetic and plastic surgery, dermatology departments, medical cosmetic outpatient departments and plastic surgery departments in general hospitals and specialized hospitals for medical cosmetic and plastic surgery, which must have obtained a "Medical Institution Business License".

[figure not shown]
### 3.5.4 Contraindications

- Do not use in patients with severe allergies manifested by a history of anaphylaxis, or history or presence of multiple severe allergies.
- Do not use in patients with a history of hypersensitivity to streptococcal proteins, as the product may contain trace amounts of such material.
- Do not use in patients with known hypersensitivity to lidocaine or to amide-type local anaesthetics.

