#### 5.2.2 Exclusion Criteria

1. Any previous non-permanent or permanent implant/filler in the hands, including autologous fat
2. Any mesotherapy or resurfacing procedure (laser, chemical peels or other ablative or non-ablative treatment) in the hands within 6 months prior to baseline
3. Any previous hand surgery including sclerotherapy
4. Any fibrosis or scarring or deformities on the hands
5. Advanced photoaged/ photodamaged skin (e.g. advanced skin elastosis, multiple lentigo solaris lesions) or skin condition with very crinkled or fragile skin on the dorsal hands
6. Subjects with active skin disease, inflammation or related conditions in the hand
7. Subjects with a history of precancerous (e.g. actinic keratosis) or cancerous lesions in the hands
8. Subjects with a history of Raynaud's disease or phenomenon, or history of other disease that may affect peripheral circulation
9. History of neurological disease that may affect peripheral neurological function
10. Subjects with a history of autoimmune disease or joint disease or connective tissue disease (e.g. rheumatoid arthritis, lupus, scleroderma etc)
11. Subjects with known hypersensitivity to any ingredient of the study product or anesthesia used in the study or with a history of any significant Adverse Events caused by dermal fillers
12. Use of topical retinoids on the dorsal hands within 6 weeks prior to baseline or use of systemic retinoids within 6 months prior to baseline
13. History of chronic lymphedema or breast cancer / mastectomy with potential to cause edema
14. Concomitant thrombolytic or anticoagulant therapy and therapy with inhibitors of platelet aggregation, (e.g. non-steroid anti-inflammatory drugs, acetylsalicylic acid, Omega 3 and Vitamin E) within 2 weeks prior to treatment, or a history of bleeding disorders. Cyclooxygenase-2 (COX-2) inhibitors are allowed
15. Treatment with chemotherapy, immunosuppressive agents, immunomodulatory therapy (e.g. monoclonal antibodies), systemic or topical (dorsal hands) corticosteroids (inhaled corticoids are allowed) within three months before study treatment
16. History of untreated epilepsy or other significant medical conditions

 EST. 1981	Title 43CH2305 CSP Vital-Lido-Hand-2w	Doc id MA-57336
---	---	---------------------------

17. Women who are pregnant or breast feeding, or Woman of childbearing potential who are not practicing adequate contraception or planning to become pregnant during the study period.

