18. Subjects participating in another interventional clinical study within 30 days of baseline
19. Subjects with unattainable expectation with regard to the aesthetic results of the treatment
20. Subjects who are involved in conducting the study (e.g. colleagues within the same department) or close relatives to any of the study staffs (e.g. parents, children, siblings or spouse ) as well as subjects who are employed by the Sponsor company, or close relatives of employees at the Sponsor company
21. Subjects with any other condition which in the opinion of the Investigator, might compromise the subject's ability to tolerate the injection procedure or comply with requirements of the study

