### 5.2.3 Screening and Subject Numbers

Each screened subject will be assigned a screening number consisting of "S" and the site number followed by a consecutive number starting with 01 at each site, e.g. S101, S102. The screening number shall be listed on a subject screening and inclusion log.

A "screening failure" is defined as a subject who does not fulfil the eligibility criteria. For screening failures, the eCRF screening visit shall be completed to an extent that makes it clear which assessments have been made and the reason why the subject did not fulfil the eligibility criteria. The reason for excluding a subject from entering the study shall also be specified in the subject screening and inclusion log.

[figure not shown]
When the Investigator has confirmed that all inclusion criteria and no exclusion criteria are met, each enrolled subject will be assigned a subject number by the eCRF consisting of the site number followed by a consecutive number starting with 01 at each site, e.g. 101, 102.

The subject number, subject name, and other information sufficient to link the eCRF to the medical records (e.g. national identification number, chart number, etc.) shall be recorded on a subject identification list. The subject identification list shall only be available at the site, both throughout and after the study.

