#### 5.6 Study Medical Device and Control Medical Device

##### 5.6.1 Study Medical Device (Investigational Product)

###### Restylane Skinboosters Vital Lidocaine

[figure not shown]
Restylane Skinboosters Vital Lidocaine is a sterile, transparent and biodegradable gel of crosslinked hyaluronic acid of non-animal origin with the addition of 0.3% lidocaine hydrochloride. It is supplied in a glass syringe with a luer-lock fitting. The product has a built in dose-guide, Smart Click™ System, which when activated creates a clicking sound and haptic feedback to indicate each injected dose. The 1 ml syringe gives approximately 100 doses of 10 µL each. The contents of the syringe are sterilized using moist heat. The exterior of the syringe, including finger grip and plunger rod are not sterile. The product is for single use only. Three disposable 29G TW (thin wall) needles, sterilized using ethylene oxide, are provided.

Composition:

- Crosslinked sodium hyaluronate 20 mg/mL
- Lidocaine hydrochloride 3 mg/mL
- Phosphate buffered saline pH 7 ad q.s. 1 mL

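### Two of the three contraindications in Protocol 3.5.4 are not named in any exclusion criterion, and the enrolment checks refer only to section 5.2

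*Protocol*

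**What the plan says.** Protocol 3.5.4 lists three contraindications, none of them qualified:

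1. "Do not use in patients with severe allergies manifested by a history of anaphylaxis, or history or presence of multiple severe allergies"
2. "Do not use in patients with a history of hypersensitivity to streptococcal proteins, as the product may contain trace amounts of such material"
3. "Do not use in patients with known hypersensitivity to lidocaine or to amide-type local anaesthetics"

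Section 3.5 as a whole describes Restylane Skinboosters Vital Lidocaine. For use of the comparator, Protocol 5.7.3 sends the reader to its own co-packed instructions for use (IFU).

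Eligibility is set out separately, as six inclusion criteria (5.2.1) and 21 exclusion criteria (5.2.2), repeated in the synopsis. The closest exclusion is number 11, which begins "Subjects with known hypersensitivity to any ingredient of the study product or anesthesia used in the study" and goes on to cover past significant adverse events from dermal fillers. Two broader exclusions are number 16, "History of untreated epilepsy or other significant medical conditions", and number 21, which starts "Subjects with any other condition which in the opinion of the Investigator".

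Under Protocol 5.2.3 a subject number is given "When the Investigator has confirmed that all inclusion criteria and no exclusion criteria are met". In 5.7.2.4, Visit 1 verifies the criteria in section 5.2; Visit 2 verifies 5.2.1 and 5.2.2 again and then randomises. SAP 4.2.2 and 4.2.3 only refer back to the protocol.

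**The concern.** The protocol says in one place who must not receive the investigational product and in another who may be enrolled, and the two lists do not match. The steps that admit a subject use only the second list. If a contraindication is missing from that list, keeping such a subject out depends on the investigator remembering a background section that the eligibility check does not cite, or on reading a broad criterion in a particular way.

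What is at stake is subject safety, not inference. Protocol 9.1.2 itself lists hypersensitivity and angioedema among post-marketing events, and counts hypersensitivity among the most commonly reported serious ones.

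**Working it through.** No arithmetic applies beyond a count. Each contraindication in 3.5.4 was set against inclusion criteria 1 to 6, exclusion criteria 1 to 21, the synopsis copy, and the steps that lead to injection. Both exclusion lists can be read in full, so redaction does not explain the result.

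**Contraindication 1: anaphylaxis or multiple severe allergies.** No criterion names it.
- Exclusion 11 applies only if the reaction was to an ingredient, to an anaesthetic used in the study, or to a dermal filler. Anaphylaxis to something unrelated falls outside it.
- Exclusion 16 has no discretionary qualifier, but it does not say which conditions count as significant.
- Exclusion 21 depends on the investigator's opinion about tolerating the procedure or complying with the study.
- Inclusion 5 asks that the subject be eligible for treatment, without defining that or pointing to 3.5.4.

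**Contraindication 2: streptococcal protein hypersensitivity.** No criterion names it.
- Exclusion 11 reaches it only if an ingredient includes trace residues. The composition in Protocol 5.6.1 opens with "Crosslinked sodium hyaluronate 20 mg/mL" and adds lidocaine hydrochloride and phosphate buffered saline; it lists no streptococcal protein. Section 3.5.4 describes the protein as material that may be present in trace amounts.
- The same general criteria (inclusion 5, exclusions 16 and 21) are available, with the same limits.

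**Contraindication 3: lidocaine or amide anaesthetics.** Exclusion 11 covers it, since lidocaine is a listed ingredient.

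Count: of 3 contraindications, 1 maps to a specific exclusion and 3 − 1 = 2 do not.

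**Steps before injection.**
- 5.2.3 and 5.7.2.4 cite only the inclusion and exclusion criteria. A screening failure is also defined in 5.2.3 by those criteria, so a contraindicated subject who meets them has no clearly defined screen-failure reason.
- 5.7.2.5 collects relevant medical history without naming allergy.
- 5.7.3.2, step 1, calls for a medical history to select patients properly, but does not cite 3.5.4.

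**Comparison with the milder cautions.** Several items that 3.5.5 lists only as warnings or precautions are firm exclusions: Raynaud's disease (8), autoimmune disease (10), bleeding disorders and anticoagulants (14), and unattainable expectations (19). The documents do not say why these were carried over to 5.2.2 when two outright contraindications were not.

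**Exposure.** Each treated subject is to receive the lidocaine product in one hand, at 0.5–1 mL (5.7.3.3), and the comparator in the other.

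**The case against.** The best reply is that 3.5.4 is already part of the protocol. An investigator who follows it will not inject such a subject. Section 11.1.1 requires the study to comply with the protocol, and 10.1 requires any deviation from it to be reported. Inclusion 5 is mandatory, and someone for whom the protocol says not to use the product is, on an ordinary reading, not eligible for treatment. A history of anaphylaxis fits exclusion 16 quite naturally. Since Protocol 3.1 says the hyaluronic acid comes from *Streptococcus* bacteria, exclusion 11 can plausibly be read to include a known residue of that source. The eCRF checklist, the Investigator's Brochure and the comparator IFU are not in the file and may deal with these groups.

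Much of this stands, and it rules out several stronger readings that a reader might infer:

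- *That the protocol directs such subjects to be treated.* It does not. The listed criteria leave the possibility open.
- *That no deviation would be recorded.* Nothing limits deviations to breaches of section 5.2, so injecting against 3.5.4 could be reported as one. What is missing is a criterion that would clearly flag the subject before randomisation.
- *That the contraindicated product goes into both hands.* Section 3.5 concerns the lidocaine product, which goes into one hand. Whether the comparator carries the same contraindications cannot be established here.
- *That the streptococcal group is plainly outside the exclusions.* This depends on how the word ingredient in exclusion 11 is read, so that half is partly an ambiguity.

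What the reply does not remove is the mismatch. The general criteria and the medical-history step allow the investigator to keep such a subject out; none of them clearly requires it.

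**Conclusion.** The point holds as an inconsistency on a safety matter within the protocol. Two of the three contraindications for the lidocaine product have no exclusion that names them, in 5.2.2 or in the synopsis, and the enrolment and Day 1 checks refer only to section 5.2. A subject in either group can meet the listed criteria, on a literal reading, and be randomised to receive in one hand a product that 3.5.4 says not to use.

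This rests on two assumptions: that exclusion 16 and inclusion 5 are too unspecific to compel exclusion, and, for the streptococcal group, that trace residues are not ingredients. If a site reads those criteria broadly, the practical gap narrows or closes, but the protocol does not tell it to. The documents give no prevalence for either group, so the number affected cannot be estimated. The hypothesis, the significance level, the sample size and the primary analysis are not affected.

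**What to change.** The sponsor must reconcile Protocol 3.5.4 with 5.2.2, the synopsis and the eligibility check at Visits 1 and 2, so that they agree on who may receive the product. Which text should change is a clinical decision for the sponsor. In doing so the sponsor should state whether the word ingredient in exclusion 11 includes trace residues, and check the result against the comparator IFU. The SAP needs no change, because it takes eligibility from the protocol by reference.

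The cost is protocol wording and any matching wording in the eCRF, with possibly a few more screen failures.

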### 3.5.5 Warnings and Precautions

#### 3.5.5.1 Warnings

- Use at specific sites where there is active disease, such as inflammation (skin eruption such as cysts, pimples, rashes or hives), infection or tumours, in or near the intended treatment site should be avoided until the underlying process has been controlled.
- Restylane Skinboosters Vital Lidocaine is only intended for use as an intradermal implant. The product should not be used for breast site injections.
- This product must not be injected intramuscularly or intravascularly. Localized superficial ischemia and necrosis with potential scarring may occur after injection in or near vessels. It is thought to result from the injury, obstruction, or compromise of blood vessels. Special caution should be taken if the patient has undergone a prior surgical procedure in the planned treatment area. Areas with limited collateral blood flow have an increased risk of ischemia.
- Unintentional intravascular injection may lead to embolization, thrombosis, occlusion of the vessels, ischemia, necrosis or infarction at the implant site or in the area supplied by the blood vessels affected. Stop the injection immediately if blanching occurs or if a patient complains of unusual pain or exhibits any symptoms suggestive of inadvertent intravascular injection. Patients should receive prompt medical attention and possibly evaluation by an appropriate specialist doctor should an intravascular injection occur.
- Patients with bleeding disorders or patients using substances that affect platelet function, thrombolytics or anticoagulants may, as with any injection, experience increased bruising or bleeding at injection site.

 EST. 1981	Title 43CH2305 CSP Vital-Lido-Hand-2w	Doc id MA-57336
---	---	---------------------------

- Special care should be taken to avoid injection into tendons in the hand as it may weaken tendons and cause tendon rupture.
- This product should not be mixed with other products prior to injection

### 3.5.5.2 Precautions

- Doctors are encouraged to discuss all potential risks of soft tissue injection with their patients prior to treatment and ensure that patients are aware of signs and symptoms of potential complications.
- This product should only be used by doctors who have appropriate training, experience, and knowledge about the anatomy at and around the site of injection in order to minimize the risks of potential complications (perforation or compression of vessels, nerves and other vulnerable structures).
- Injection procedures are associated with a risk of infection. Aseptic technique and standard practice to prevent cross-infections are to be followed.
- Use with caution in patients with risk factors for developing hand skin irritation.
- Use in dorsal hand in patients with disease, injuries or disabilities of the hand has not been studied. Care should be used in treating patients with autoimmune disease affecting the hand, Dupuytren's contracture, history of hand tumour, vascular malformations, Raynaud's disease and patients at risk for tendon rupture.
- Avoid injecting into areas with, or in close proximity to, prior implants other than sodium hyaluronate, as this could aggravate latent adverse events or interfere with the aesthetic outcome of the treatment.
- Large bolus injection, injecting too superficially and injections in areas with limited soft tissue support or soft tissue cover, or thin skin, may result in contour irregularities and palpable lumps and/or bluish discolouration.
- Inflammatory pigmentation changes and scarring might occur following soft tissue injections. Patients with abnormal wound healing or dark skin (Fitzpatrick Type IV–VI) may be more prone to developing hypertrophic scarring and keloid formation.
- Injection procedures can lead to reactivation of latent or subclinical herpes viral infections.
- This product should be used with caution in patients with autoimmune disease or on immunosuppressive therapy.
- Patients with unattainable expectations are not suitable candidates for treatment.
- This product is packaged for single patient and single session use only and should be discarded immediately after use. Do not resterilize or reuse the product in order to avoid risks of infections.
- Do not use the product if package is opened or damaged, or if the expiry date or lot number is illegible.
- Patients should avoid excessive sun, UV lamp exposure and extreme temperatures at least until any initial swelling and redness have resolved.
- If laser treatment, chemical peeling or any other procedure based on active dermal response is performed after treatment with this product, there is a theoretical risk of eliciting an inflammatory reaction at the implant site. This also applies if the product is administered before the skin has healed completely after such a procedure.
- The safety for use during pregnancy, in breastfeeding females or in patients under 18 years has not been established.

GALDERMA <small>EST. 1981</small>	Title 43CH2305 CSP Vital-Lido-Hand-2w	Doc id MA-57336
---	---	---------------------------

- The product contains lidocaine. If additional nerve block or topical lidocaine or other local anesthetics or agents structurally related to amide-type local anesthetics are used concurrently with the product the following considerations should be observed:
  - Use with caution in patients with epilepsy, impaired cardiac conduction, severely impaired hepatic function or severe renal dysfunction.
  - High doses of lidocaine (more than 4.5 mg/kg of bodyweight) can cause acute toxic reactions manifesting as symptoms affecting the central nervous system and cardiac conduction.
  - Systemic toxic effects could be additive.

## 4 Study Objectives

[figure not shown]
### 4.1 Primary Effectiveness Objective

To demonstrate that Restylane Skinboosters Vital Lidocaine is associated with less pain than Restylane Vital when injected in the dorsal hand for improvement of appearance.

*Endpoint:*

- The within-subject difference in VAS score (Restylane Skinboosters Vital Lidocaine - Restylane Vital) at end of injection (T0).

CCI

2024-03-13 11:45

Effective date:

Effective

Version: 3.0

GALDERMA EST. 1981	Title 43CH2305 CSP Vital-Lido-Hand-2w	Doc id MA-57336
-----------------------	---	---------------------------

CCI

[REDACTED]

[REDACTED]

[REDACTED]

[REDACTED]

[REDACTED]

[REDACTED]

#### 4.4 Exploratory Objective

Not applicable

### 5 Study Design

#### 5.1 Overall of Study Design and Rationale

[figure not shown]
##### 5.1.1 Overall Study Design

This is a randomized, multi-center, split-hand, subject-blinded study comparing pain, safety and effectiveness of Restylane Skinboosters Vital Lidocaine and Restylane Vital without lidocaine for improving appearance of the dorsal hands in Chinese subjects.

Written informed consent will be obtained before any study related procedure is performed. Subjects will be screened for eligibility within 14 days prior to study randomization on Day 1. The Screening Visit and Baseline Visit can be performed on the same day.

Each subject will receive treatment on Day 1 with Restylane Skinboosters Vital Lidocaine® in one hand and Restylane Vital in the opposite hand, as randomly assigned. Study treatment will be unblinded for the Treating Investigator. The first injection will always start in the right hand. No topical or local anesthetic or other pain-relieving medication should be used before all Visual Analogue Scale (VAS) assessments are completed. Ice for pain relief is allowed and should be applied equally on both hands before treatment, and an approximately two-minute ice application time per hand is recommended. Ice may also be used after all VAS evaluations have been completed. The second treatment, that is the injections in the left hand, will be performed after the treatment of the first (right) hand and the VAS assessment at T0 of the right hand is completed.

The subject will assess pain experienced directly after treatment on a 100 mm VAS at the end of each treatment (before massaging the treatment area). The time should be recorded in the electronic Case Report

 EST. 1981	Title 43CH2305 CSP Vital-Lido-Hand-2w	Doc id MA-57336
---	---	---------------------------

Form (eCRF) and the pain will thereafter be assessed by the subject at  $10\pm3$ ,  $20\pm3$ , and  $30\pm3$  minutes on the VAS after the treatment on the right and left hand, respectively.

After the treatment of each hand is finished, and after the T0 pain assessment is complete, massage can be performed on the treated area of that hand. It is recommended not to exceed five minutes of massage to avoid affecting subsequent VAS assessments. It is not necessary to massage both hands simultaneously.

A safety follow-up telephone call should be made 72 hours after treatment.

CCI

CCI

CCI

